It is well documented that atrial fibrillation confers an increase in an individual's risk of stroke. This risk is based on a number of variables and importantly is measured over a number of years of suffering with the diagnosis. Short duration atrial fibrillation does not confer this risk. International guidance regarding management of clinical atrial fibrillation suggests that it takes more than 24 hours for the formation of intra-cardiac thrombus which is the mechanism for stoke risk(5). In individuals where atrial fibrillation is induced and present for only a short duration (more than 15 minutes but less than 20 minutes), left atrial mechanical dysfunction resolves immediately after return to sinus rhythm even in a very high risk population(51). This removes the concern that there may be ongoing increase risk even after restoration of sinus rhythm.

The study by Sparks et al also addresses the concern that the use of direct current cardioversion may induce atrial "stunning" and so a risk of stroke in the time directly after. This is not the case with short duration atrial fibrillation as mechanical function immediately returns to baseline in both those returning to sinus rhythm spontaneously and those returned by DC cardioversion(51). Immediate DC Cardioversion of arrhythmia within the context of the cardiac electrophysiology laboratory is known to be safe and effective(52).

Where a participant is not already on anticoagulant therapy and has had short duration atrial fibrillation induced, there is no need for anticoagulation regardless of the mechanism of their return to sinus rhythm or background stroke risk.

Cessation of antiarrhythmic medications

We will be asking participants to stop any medications that control the rhythm of the heart for 6 half lives before each study infusion administered in Part A of the protocol. During these few days participants may experience a worsening of any palpitation symptoms. We do not believe this short cessation of medication confers any long term threat to the participants. Recruits are told of the risk and are advised that they "should consider this point carefully before agreeing to take part". Although symptoms may worsen for those few days, we would expect things to return to normal once the tablets are restarted after the study visit.

Benefits of Involvement in Study

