All parts of this investigation utilise a standard infusion protocol of a study drug. This study drug will be isoprenaline or placebo delivered in a double blinded fashion or will be open label isoprenaline dependent on which experiment it is being administered for. In all cases the infusion protocol will be identical as will the associated outcomes recorded. Although different experiments within the protocol call for different, statistically driven endpoints, the endpoints for every administration of a study drug infusion protocol are the same.

Outcome after which infusion would be stopped

- Occurrence of atrial fibrillation lasting greater than 30 seconds during study drug infusion protocol
- Occurrence of an arrhythmia other than atrial fibrillation, sinus tachycardia or junctional rhythm lasting greater than 30 seconds during study drug infusion protocol
- Discontinuation of the study drug infusion
 - o Severe tremulousness or anxiety
 - Complaints of severe chest tightness
 - Decrease in systolic blood pressure to consistently < 70mmHg
 - Electrocardiographic changes suggestive of myocardial ischaemia

Pre-specified outcomes to be recorded but which would not trigger cessation of infusion

- Occurrence of atrial fibrillation lasting less than 30 seconds during study drug infusion protocol
- Occurrence of an arrhythmia other than atrial fibrillation, sinus tachycardia or junctional rhythm lasting less than 30 seconds during study drug infusion protocol
- Time from start of infusion protocol to occurrence of atrial fibrillation
- Rate of infusion at time of occurrence of atrial fibrillation
- Maximum tolerated rate of study drug infusion prior to its cessation for any reason

Safety Endpoints associated with each infusion administration

- Death within 24 hours of start of study drug infusion protocol
- Stroke within 24 hours of start of study drug infusion protocol
- Myocardial Infarction within 24 hours of start of study drug infusion protocol

Observational Data

Collected from Additional Monitoring Group

Participants from some groups recruited will be offered the chance to have some additional follow up monitoring after their ablation procedure. This data will be purely descriptive and unpowered. It will be analysed looking at the following endpoints.

Observational Endpoints

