- Ongoing angina symptoms without investigations demonstrating the absence of myocardial ischaemia
- Left ventricular ejection fraction measured at <30%
- Symptoms of decompensated heart failure syndrome in the last 3 months
- Severe obstructive lung disease
- Pregnancy at the time of enrolment or a desire to become pregnant during the study period
- Women who are breastfeeding
- Reduced life expectancy not associated with cardiovascular disease (less than 1 year)
- Unable to provide informed consent

Group 1 – Paroxysmal Atrial Fibrillation Group

- Any past history of episode of persistent atrial fibrillation at the time of enrolment to the study
- Treatment with any antiarrhythmic agent within six half-lives of that agent from before an administration of the study drug infusion

Group 2 – SVT Ablation Group

- Any past history of atrial fibrillation documented on 12 lead ECG or ambulatory ECG monitor
- Any past history of atrial flutter documented on 12 lead ECG or ambulatory ECG monitor
- Characterisation of SVT as any arrhythmia other than ANRT or AVNRT
- Treatment with any antiarrhythmic agent within six half-lives of that agent from the ablation procedure (including intra-procedural use) with the exception of isoprenaline and adenosine

Group 3 – Atrial Flutter Ablation Group

- Characterisation of arrhythmia as any arrhythmia other than cavo-tricuspid isthmus dependent atrial flutter at the time of ablation
- Treatment with any antiarrhythmic agent within six half-lives of that agent from the ablation procedure (including intra-procedural use) with the exception of isoprenaline and adenosine

Group 4 – Pulmonary Vein Isolation Group

- Requirement for a more extensive ablation strategy than pulmonary vein isolation alone
- Intra-procedural treatment with any antiarrhythmic agent with the exception of isoprenaline and adenosine
- Treatment with any antiarrhythmic agent in the days before the ablation within six half-lives of that agent from the ablation procedure

Participant Information

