Central to this project is the delivery of a standardised infusion protocol. This infusion will be an open label isoprenaline infusion in some parts of the project or will be a study drug infusion of either isoprenaline or placebo (normal saline) in other parts of the project. In all cases, each administration of an infusion will follow this protocol.

The infusion will be delivered to subjects in the supine position. Minimum monitoring of the participant at the time of the infusion will include non-invasive blood pressure monitoring at 1 minute intervals, continuous ECG monitoring, continuous monitoring of pulse oximetry and direct observation of the subject by a member of the study team. A blood sample to measure markers of response to the infusion may be taken during the infusion protocol, however such samples are an optional part of the consent process and do not constitute a core part of the study.

The study drug infusion will be drawn up in compliance with local policies regarding intravenous medications. Unblinded members of the nursing staff will identify whether the participant has been randomised to an isoprenaline infusion or to placebo. They will then draw up either 40 mls of normal saline (placebo infusion) into a 50 mls luer lock syringe or will make up the isoprenaline infusion in a 50 mls luer lock syringe. For the isoprenaline infusion, two ampules of isoprenaline sulphate, each containing 10 mls of 0.01 mg/ml solution will be added to 20 mls of normal saline. This will create 40 mls of 0.005mg/ml (5 micrograms/ml) solution containing a total of 0.2mg (200micrograms) isoprenaline sulphate.

The two infusions will be visually identical. The syringe will be labelled with the participant's candidate number, hospital number, name and date of birth but not with the syringe contents. All other cardiac electrophysiology laboratory staff and the study team will remain blinded. Unblinded nursing staff may attach and deliver the study drug infusion, however they should not be the nurse named to monitor the participant and they will not contribute to determination or recording of any study data. This process will only be required in the cardiac electrophysiology laboratory environment as all placebo controlled infusions will take place in this setting.

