The minimum staff required to administer the infusion will include a registered nurse considered competent with administration of intravenous medications (as judged by the hospital trust at which the infusion is being delivered) and a licensed medical practitioner considered experienced in the field of cardiology and who is a certified Advanced Life Support provider.

Prior to administration of the study drug infusion, the study team will assess the participant regarding their potential suitability for use of antiarrhythmic medications in the event that atrial fibrillation which persists for greater than 10 minutes is induced.

The route of administration will depend on the situation in which the infusion is being administered. Where the infusion is being administered in a ward based environment, it is anticipated that the infusion will be delivered via a peripherally sited intravenous cannula usually sitting in an antecubital fossa vein. Where the infusion is being given in the Cardiac Electrophysiology Laboratory, it will usually be administered via a central venous sheath sited in the femoral vein. Standard aspetic technique associated with the administration of intravenous drugs will be applied in all settings to comply with local policy.

The study drug infusion will be delivered following a modified version of the scheme previously published by Morady and colleagues(30). As their study suggested an accelerating rate of induction up to the maximum dose delivered (20mcg/min), to allow for the potential effect of our study using the sulphate form of the drug rather than the hydrochloride and given the documented favourable tolerability profile of the infusion, we have elected to add a further dose increment to our protocol. This remains within the FDA approved dosing regimen for the drug.

The protocol will be..

- Infusion started at 5mcg per minute for 2 minutes
- Increased to 10mcg per minute for 2 minutes
- Increased to 15mcg per minute for 2 minutes
- Increased to 20mcg per minute for 2 minutes
- Increased to 25mcg per minute for 2 minutes
- Infusion is then stopped and subject is monitored over a 10 minute washout phase

Subjects will either follow the protocol to its completion or will reach one of the pre-defined infusion endpoints at which point the infusion will be stopped. These endpoints as described previously are..

Outcome after which infusion would be stopped

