- Occurrence of atrial fibrillation lasting greater than 30 seconds during study drug infusion protocol
- Occurrence of an arrhythmia other than atrial fibrillation, sinus tachycardia or junctional rhythm lasting greater than 30 seconds during study drug infusion protocol
- Discontinuation of the study drug infusion
 - Severe tremulousness or anxiety
 - Complaints of severe chest tightness
 - Decrease in systolic blood pressure to consistently < 70mmHg
 - Electrocardiographic changes suggestive of myocardial ischaemia

The diagnosis of atrial fibrillation will rest with the clinician acting as operator for the procedure aided by the attending cardiac physiologists.

If a subject experiences an arrhythmia lasting greater than 30 seconds and thus triggering the infusion to stop, they will be monitored for 10 minutes. It is anticipated from previous literature that in the majority of cases, subjects will have spontaneously reverted to normal sinus rhythm after this period of time. It is accepted however that in some cases an arrhythmia will persist beyond this point and in those cases, the supervising physician will restore sinus rhythm.

All subjects will be monitored for at least 30 minutes after an infusion administration.

At all infusions, the following data will be recorded

- Level of sedation at the start of the infusion (AVPU score)
- Total dose of sedation given in the 20 minutes prior to the start of the infusion

- The presence or absence of an episode of arrhythmia lasting greater than 30 seconds
 - The diagnosis for the arrhythmia seen
 - The time from initiation of the infusion to the start of the episode of arrhythmia lasting greater than 30 seconds
 - The time from the start of the episode of arrhythmia lasting greater than 30 seconds to the restoration of sinus rhythm
 - The method of restoration of sinus rhythm
- The presence or absence of one of the other reasons for stopping the infusion
 - The reason for stopping the infusion
- The time from the start of the infusion to its cessation for whatever reason
- The maximum rate of infusion delivered to the study subject
- Minute by minute heart rate and blood pressure measurements over the course of the infusion
- The presence of episodes of arrhythmia lasting less than 30 seconds
 - The diagnosis for each arrhythmia seen
 - The time from initiation of the infusion to the start of each episode of arrhythmia lasting less than 30 seconds

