If arrhythmia persists for greater than 10 minutes, it will be at the discretion of the attending clinician to decide whether to perform DC cardioversion, continue to wait or to proceed with the intended ablation procedure. If the participant is in persistent arrhythmia at the time of the start of the preablation infusion (most likely to occur in the atrial flutter ablation group) then that infusion will not be performed and the operator will proceed to the ablation procedure. Such participants will receive the post-ablation infusion as per protocol.

After the pre-ablation study drug infusion, the attending clinician will then proceed to the clinically indicated ablation procedure. The diagnosis and endpoint for the ablation procedure will be
recorded. When the attending physician is confident they have achieved their endpoint for the procedure, efforts will be made to induce a similar level of sedation as that recorded at the time of the pre-ablation study drug infusion. It is accepted that this may not be possible in the real world setting.

Once efforts have been made to achieve a similar level of sedation, the post-ablation study drug infusion will be administered using the standard infusion protocol for the identical infusion delivered prior to ablation.

All patients will be expected to leave the cardiac electrophysiology laboratory with a heart rate approaching that seen at baseline (if in sinus rhythm at the start of the procedure) and in sinus rhythm. It is accepted that some patients will require DC cardioversion if atrial fibrillation occurring during the infusion protocol persists for greater than 10 minutes.

It is also anticipated that it may be difficult for participants to tell whether they are undergoing a part of the study protocol or a part of their NHS ablation procedure at any particular time once they have entered the Cardiac Electrophysiology Laboratory. This is due to the use of sedation and the similarity between the participant experience in each part of the procedure. The potential for confusion will be clearly explained in the patient information sheet.

• Part B - Visit 3 – 6 week follow up

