The investigators are authorised to provide alternative treatment to that specified in the protocol at any stage if he/she feels it is in the participant's best interest. The reasons for deviation from protocol should be recorded.

Reasons for Discontinuation of Subject's Participation in Study

A subject can voluntarily discontinue their involvement in the study at any stage without the need to give reason and without prejudicing further treatment. In addition, subjects will be removed from the study if they cease to meet the inclusion criteria after enrolment (eg participant in SVT block has electrophysiology study that demonstrates atrial tachycardia rather than ANRT or AVNRT) or if they develop one of the exclusion criteria (eg require treatment with amiodarone in the time between the 2 infusions required for Protocol Part A). Subjects will also be excluded from continuation in the study if they develop anaphylaxis, chest pain or ECG features of myocardial ischaemia during the infusion protocol.

Where subjects withdraw or are excluded from the study after enrolment but prior to their completion of the study schedule, a further subject will be recruited to their subject group to take their place. Any data collected before withdrawal may be included in the study results.

End of Study Actions

Having withdrawn from the study, been excluded from continued participation or having completed their final visit or ambulatory ECG recording, participants will have completed their involvement in the study. There are no specific interventions required at completion of the study schedule. All participants will be informed that they may still contact the study team should they have questions or concerns regarding their health or their involvement in the study.

Safety Assessment

Adverse Events

Definitions

- Adverse Event (AE): any untoward medical occurrence in a patient or clinical study subject.
- Serious Adverse Event (SAE): any untoward and unexpected medical occurrence or affect that:
 - Results in death
 - Is life-threatening refers to an event in which the subject was at risk of death at the time of the event; it does not refer to an event which hypothetically might have caused death if it were more severe
 - Requires hospitalisation, or prolongation of existing inpatients' hospitalisation
 - Results in persistent or significant disability or incapacity
 - o Is a congenital anomaly or birth defect

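### Part B contradicts the common infusion protocol on induced arrhythmia lasting over 10 minutes, leaving open how AF carried into the post-ablation infusion is counted and whether participants treated for induced AF stay in the analysis

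*Protocol*

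**What the plan says.** **The common procedure.** The Infusion Endpoints section states: "In all cases the infusion protocol will be identical as will the associated outcomes recorded". The Infusion Protocol section repeats it: "In all cases, each administration of an infusion will follow this protocol". After a triggering arrhythmia and 10 minutes of monitoring, that section accepts that "in some cases an arrhythmia will persist beyond this point and in those cases, the supervising physician will restore sinus rhythm". Part A repeats the instruction at both infusion visits.

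**Part B.** Under Part B - Visit 2 - Ablation Procedure, after 10 minutes "it will be at the discretion of the attending clinician to decide whether to perform DC cardioversion, continue to wait or to proceed" to the ablation. Participants are expected to be in sinus rhythm when they leave the laboratory. A persistent arrhythmia at the start of the pre-ablation infusion means that infusion is omitted. For the post-ablation infusion only the sedation level is to be matched; no rhythm condition is given.

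**Safety text.** Administration of Isoprenaline answers the labelled tachyarrhythmia contraindication by saying the drug will not be given during tachyarrhythmia. Induced episodes of atrial fibrillation cites recovery of atrial mechanical function after AF "present for only a short duration (more than 15 minutes but less than 20 minutes"), sees no need for anticoagulation after short AF, and separately states that thrombus takes more than 24 hours to form.

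**Antiarrhythmic drugs.** Before each infusion the team assesses "potential suitability for use of antiarrhythmic medications in the event that atrial fibrillation which persists for greater than 10 minutes is induced". For Group 4 the Exclusion Criteria list "Intra-procedural treatment with any antiarrhythmic agent with the exception of isoprenaline and adenosine"; Groups 2 and 3 carry an equivalent exclusion. Reasons for Discontinuation removes subjects "if they develop one of the exclusion criteria", replaces them, and makes inclusion of their earlier data optional.

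**The concern.** Staff cannot follow both instructions, and three consequences follow.

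1. **Endpoint.** The post-ablation infusion supplies the primary endpoint of Experiments 3 and 4 and half of the paired endpoint of Experiments 5 and 6. If AF from the first infusion is still running, the text does not settle whether it is an occurrence of AF during the second. The same drug is given both times, so this arises mainly on isoprenaline.
2. **Safety argument.** The supporting evidence concerns shorter AF than the Part B text permits. Starting isoprenaline in a participant still in AF would contradict the protocol's own answer to the labelled contraindication.
3. **Retention.** A participant whose induced AF is treated with a foreseen drug can be removed and replaced. Retention then depends on an outcome of the study infusion.

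**Working it through.** **Can AF persist into the second infusion?** The common text restores sinus rhythm after 10 minutes; the Part B text allows waiting or proceeding. The Part B rhythm check applies only to the first infusion. The permitted sequence is therefore induced AF, ablation in AF, then second infusion. The only later limit is the expectation of sinus rhythm at exit, which comes after that infusion.

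**Duration.** The usual-care table gives 120 minutes of intervention time for the ablation. 10 + 120 = about 130 minutes of AF if the operator proceeds and AF does not end. That exceeds the 15 to 20 minutes cited and is far below 24 hours (1,440 minutes).

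**Participants at risk.** Inputs: 35 per group (Experiments 3 and 4), and expected AF rates of >30% v <5% (Experiment 3) and <10% on isoprenaline (Experiment 4). I assume the Experiment 3 rates also hold before ablation. Assumption not in the documents: 10% to 30% of induced AF is carried through ablation.

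| | AF at first infusion | Carried over (10% to 30%) |
|---|---|---|
| Flutter, isoprenaline | 0.30 × 35 = 10.5 | 1.05 to 3.15 |
| Flutter, placebo | 0.05 × 35 = 1.75 | 0.18 to 0.53 |
| SVT, isoprenaline | under 0.10 × 35 = 3.5 | under 0.35 to 1.05 |

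**How many are misclassified?** Only those who would not have had AF at the second infusion anyway. Experiment 5 expects 10% disagreement, 0.10 × 35 = 3.5 pairs.

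- Split evenly by direction, 1.75 of the 10.5 change from AF to no AF (one sixth). With 1 to 3 carried over, 0.2 to 0.5 are misclassified.
- If all disagreement runs that way, 3.5 of 10.5 (one third) gives 0.3 to 1.0.
- If none of those carried over would have had AF again, all 1 to 3 are misclassified. This is the worst case, 1/35 to 3/35, or 3 to 9 percentage points on the isoprenaline rate.

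In the paired endpoint, AF before and carried-over AF after scores as no change, which favours the claim of under 20% disagreement.

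**When does that decide Experiments 5 and 6?** One-sided 95% upper limits with n = 35; Wald is p + 1.645 × √(p(1 − p)/35):

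| Changes | Wald | Exact |
|---|---|---|
| 2 | 0.122 | 0.169 |
| 3 | 0.164 | 0.207 |
| 4 | 0.203 | 0.243 |

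The verdict turns between 3 and 4 changes (Wald) or 2 and 3 (exact). One pair matters there and nowhere else.

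**Stress case for Experiment 3.** Assume a true post-ablation rate of 5% in both arms, with a fraction f of those induced before ablation counted again. The rates become 0.05 + 0.95 × 0.30 × f and 0.05 + 0.95 × 0.05 × f. With f = 10% they are 7.9% v 5.5%; with f = 25%, 12.1% v 6.2%. By normal approximation, the chance of a significant result favouring isoprenaline rises from 2.5% to about 6% and 13%. This is a deliberately unfavourable scenario.

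**The case against.** - **The Part B text is setting-specific.** The common text sets no deadline for restoring sinus rhythm, and the Part B text expects it by exit. This narrows the conflict. It does not remove it, because two sections say that the procedure is the same in all cases and neither allows an exception.
- **The safety case survives.** A reader might infer that proceeding in AF leaves the stroke argument without support. The documents do not bear that out: the 24-hour thrombus statement still applies to about 130 minutes, and 120 minutes is a usual-care procedure time, not an AF duration. What lacks cover is the mechanical-function evidence and the reach of the short-AF anticoagulation statement.
- **Occurrence naturally means onset.** The time from infusion start to episode start is recorded, and it has no sensible value for AF already present. So the text permits counting carried-over AF but does not direct it. It remains open, because nothing requires sinus rhythm at the post-ablation start.
- **The drug route and the carry-over route rest on different readings.** True: the Part B options name no drug. The two should not be added together. The drug conflict stands alone, between the suitability assessment and the exclusion and replacement rules.
- **AF at the first infusion is not the primary event of Experiments 3 and 4.** Correct, and AF treated after the second infusion is already recorded. But removal after the first infusion still costs those experiments participants shown to be inducible, and it breaks the pairs in Experiments 5 and 6. Use of earlier data is only optional.
- **Sensitivity analyses belong in the SAP.** Fair in general. The endpoint wording and the replacement rule, however, are fixed here.

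**Conclusion.** The contradiction is explicit, and so is the conflict between foreseen antiarrhythmic treatment and the removal rule. The carry-over problem is possible, not established.

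Its size is not in the documents. On the protocol's expected rates, the assumed 10% to 30% carry-over and 10% disagreement, it is likely 0 to 1 misclassified participants per experiment. One to three is a worst case confined to the flutter group; the SVT group, with an expected rate under 10%, gives about one at most. Reversion or cardioversion before the second infusion would lower all these figures, and the protocol expects most episodes to revert within 10 minutes.

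Two wider readings are not supported. The concern is not AF present before any infusion, since the pre-ablation infusion is then omitted. Nor does carry-over appear to reach Experiment 2: post-isolation data are described as secondary, so that experiment seems to rest on the pre-ablation infusion. The removal rule does reach Group 4. Experiment 4 is declared descriptive, so less depends on it.

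This should be corrected because the change is cheap and the bias, where it arises, depends on the arm.

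**What to change.** Reconcile Administration of Isoprenaline, Induced episodes of atrial fibrillation, the Part B Exclusion Criteria, Infusion Protocol and Part B - Visit 2 so that one instruction applies and the safety text matches what it permits. Which clinical rule applies is for the sponsor to decide.

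For the analysis, add two statements:

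1. Only AF with onset after the start of the infusion concerned counts as induced by it. Participants already in AF when the post-ablation infusion is due to start are reported separately, with a sensitivity analysis that counts them both ways.
2. An infusion outcome already recorded stays in the analysis whatever treatment follows. No participant's event is dropped or replaced because the induced arrhythmia was treated.

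The second statement concerns recorded outcomes only. It does not decide whether a treated participant goes on to a further infusion.

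Cost: wording in a few paragraphs, one endpoint rule and one sensitivity analysis. No change in sample size.
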